# **Primary Safety Endpoints:**

The number and proportion of participants reporting the following events will be assessed:

- Solicited local adverse events, including redness / erythema, swelling / induration, pain, and limitation of arm movement within 30 minutes of vaccination and over the 3-day period post-vaccination (Days 0-3).
- Solicited systemic adverse events, including fever, fatigue/malaise, muscle aches, joint aches, chills, nausea, and headache within 30 minutes of vaccination and over the 3-day period post-vaccination (Day 0-3).
- Unsolicited Adverse Events (AEs) occurring within 90 days post-vaccination.
- Serious Adverse Events (SAE) occurring during the entire study period (Days 0-90).

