Counts and percentages of subjects with solicited local and systemic reactions during the three days post-injection. In addition, all adverse events (AE) and serious adverse events (SAEs), and new onset of chronic diseases (NOCDs) will be collected for the entire study period. Specifically, the following safety parameters will be monitored and analyzed in terms of the number and proportion of participants reporting the following events will be assessed:

- Solicited local adverse events, including redness/erythema, swelling/induration, pain and limitation of arm movement within 30 minutes of vaccination and over the 3-day period post vaccination (Day 0-3).

- Solicited systemic adverse events, including fever, fatigue/malaise, muscle aches, joint aches, chills, nausea and headache within 30 minutes of vaccination and over the 3-day period post vaccination (Day 0-3).

- Unsolicited adverse events (AEs) occurring within 90 days post vaccination.

- Serious Adverse Events (SAE) occurring during the entire study period (Days 0-90).

Counts of all events will be reported and summarized according to event severity, as "any local AE", or "any systemic AE", and by relationship to administration of study product, as deemed by a blinded study clinician. Percentages of participants experiencing each reaction or event, or at least one reaction or event will be calculated along with two-sided exact 95% CIs. The percentage of participants with solicited AE and SAEs will be compared between vaccine and comparator groups and a two-sided p-value of 0.05 will be considered statistically significant.

Inferential analyses

GMT ratios (GMT active comparator vaccine/GMT GPO TRI FLUVAC) and difference of seroconversion rate (with two-sided 95% CI) related to the comparisons of interest will be computed. Acceptance value of GMT ratios at \leq 1.5 and/or difference of seroconversion rate at \leq 10% for the upper bound of the 95% CI will be considered for non-inferiority.

Secondary Immunogenicity Endpoints and analysis:

The secondary immunogenicity endpoints will be analyzed by the following:

- Number and percentage of participants with a HI antibody titer $\geq 1:40$ (seroprotective level) to each of the three vaccine antigens measured on Day 21 and Day 90.

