Description of active comparator vaccine:

a Licensed Influenza vaccine (seasonal trivalent inactivated split virion influenza vaccine recommended for Southern hemisphere in 2017 (consisting of A/Michigan/45/2015 (H1N1) pdm-09-like virus, A/Hong Kong/4801/2014 (H3N2) - like virus, and B/Brisbane/60/2008-like virus) 0.5 mL administered intramuscularly (IM) in the deltoid muscle.

Study Summary

FREF 01: Study Profile

FREF 02: Number and Percentage of Cases with Adverse Events

FREF 03: Number and Percentage of Adverse Events by Systemic Organ Class (by Each Group)

FREF 04: Number and Percentage of Cases with Adverse Events by Systemic Organ Class (by Each Group)

FREF 06: Summary Number and Percentage of Cases by Temperature Grading at Post Immunization

FREF 07: Number and Percentage of Local Reaction Grading at Post Immunization

Note: Erythema and Induration will be not included.

FREF 08: Number and Percentage of Systemic Reaction Grading at Post Immunization

Measure	Study Group	HAI Assay		
Masure	Study Group	Flu A H1 antibody titer	Flu A H3 antibody titer	Flu B antibody titer
Day 21				
Sero-conversion Rate ^a	Tri fluvac (N=)	xx.xx (xx.xx, xx.xx)	xx.xx (xx.xx, xx.xx)	xx.xx (xx.xx, xx.xx)
	Comparator (N=)	XX.XX (XX.XX, XX.XX)	XX.XX (XX.XX, XX.XX)	xx.xx (xx.xx, xx.xx)
	P-value =	X.XXXX	X.XXXX	X.XXXX
Sero-protection Rate ^b	Tri fluvac (N=)			
	Comparator (N=)			
	P-value =			
GMT ^c	Tri fluvac (N=)			
	Comparator (N=)			
	P-value =			
GMFRs ^d	Tri fluvac (N=)			
	Comparator (N=)			
	- · /			
Day 90				
Sero-conversion Rate ^a	Tri fluvac (N=			
	Comparator (N=)			
	P-value =			
Sero-protection Rate ^b	Tri fluvac (N=)			
-	Comparator (N=)			

TREF 01: Summary of Sero-conversion, Sero-protection, GMT and GMFRs

P-value =

TREF 01: Summary of Sero-conversion, Sero-protection, GMT and GMFRs (Continue)

Measure	Study Group	HAI Assay			
		Flu A H1 antibody titer	Flu A H3 antibody titer	Flu B antibody titer	
GMT ^c	Tri fluvac (N=)				
	Comparator (N=)				
	P –value =				
GMFRs ^d	Tri fluvac (N=)				
	Comparator (N=)				

Note: a Sero-conversion is defined as 4 fold rising titer from baseline (Day 0). Values are the percent of subjects in each group (with 95% CI).

^b Sero-protection is defined as a HAI titer \geq 40; values are the percent of subjects in each group (95% CI) with a HAI titer \geq 40.

^c Values are the geometric means titer (GMT) (with 95% CI) for the subjects in each group.

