	Tri fluvac (N = xx)	Comparator (N = xx)	Tri fluvac (N = xx)	Comparator (N = xx)	Tri fluvac (N = xx)	Comparator (N = xx)	Tri fluvac (N = xx)	Comparator (N = xx)
Min, Max								
P- value =								

	D	Day 0 Day 7		Day 21		Day 90		
	Tri fluvac (N = xx)	Comparator (N = xx)	Tri fluvac (N = xx)	Comparator (N = xx)	Tri fluvac (N = xx)	Comparator (N = xx)	Tri fluvac (N = xx)	Comparator (N = xx)
HEENT, n (%)								
Normal	xx(xx.xx)	xx(xx.xx)						
Abnormal	xx(xx.xx)	xx(xx.xx)						
P- value =	X.2	xxxx						
Lungs, n (%)								
Normal								
Abnormal								
P- value =								
Cardiovascular, n (%)								
Normal								
Abnormal								
P- value =								
Gastrointestinal, n (%)								
Normal								
Abnormal								
P- value =								
Musculoskeletal, n (%)								
Normal								
Abnormal								
P- value =								
Skin, n (%)								
Normal								
Abnormal								
P- value =								

TREF 3.4: Physical Examination by GPO Tri Fluvac and Active Comparator Group

	Day 0		D	Day 7		Day 21		Day 90	
	Tri Fluvac (N = xx)	Comparator (N = xx)	Tri Fluvac (N = xx)	Comparator (N = xx)	Tri Fluvac (N = xx)	Comparator (N = xx)	Tri Fluvac (N = xx)	Comparator (N = xx)	
Neurologic, n (%)	X	((
Normal	xx(xx.xx)	xx(xx.xx)							
Abnormal	xx(xx.xx)	xx(xx.xx)							
P- value =	X XXXX								

TREF 3.4: Physical Examination by GPO Tri Fluvac and Active Comparator Group (Continue)

TREF 3.5: Comparison of Maximum Grade of Any Local Reaction at Post Immunization by GPC
Tri fluvac and Active Comparator Group

Grade		Tri Fluvac (N = xx) n (%)	Comparator (N = xx) n (96)
Grada 0			
Grade 0		XX(XX.XX)	XX(XX.XX)
Grade 1		XX(XX.XX)	XX(XX.XX)
Grade 2		xx(xx.xx)	xx(xx.xx)
Grade 3		xx(xx.xx)	xx(xx.xx)
P- value =	X.XXXX		

Note: - Any local reaction on any day (by case)

- Erythema and Induration will be not included.

- Grading

- Grade 0 none
- Grade 1 mild
- Grade 2 moderate
- Grade 3 severe

TREF 3.6: Comparison of Local Reaction at Post Immunization each Follow up Time by GPO Tri Fluvac and Active Comparator Group

	30	min	D	Day 1	D	ay 2	Da	ny 3
Local Reaction	Tri Fluvac	Comparator						
	(N=xx)							
- Pain, n (%)	xx(xx.x)	xx(xx.xx)						
p-value =	X.:	xxxx						
- Limitation of arm movement, n (%)								
p-value =								
- Erythema (cm.)								
n								
Mean(SD)								
Median								
Min, Max								
p-value =								
- Swelling (cm.)								
n								
Mean(SD)								
Median								
Min, Max								
p-value =								
- Induration (cm.)								
n								
Mean(SD)								

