Median								
Min, Max								
p-value =								

Note: - Summary by case who had symptoms

TREF 3.7: Comparison of Maximum Grade of Local Reaction by Symptom at Post Immunization
by GPO Tri fluvac and Active Comparator Group

Lo	ocal Reaction		Tri fluvac (N=xx)	Comparator (N=xx)
Pain,	n (%)			
Grad	de 0		xx(xx.xx)	xx(xx.xx)
Grad	de 1		XX(XX.XX)	xx(xx.xx)
Grad	de 2		xx(xx.xx)	xx(xx.xx)
Grad	de 3		XX(XX.XX)	xx(xx.xx)
	p-value =	X.XXXX		
Limi	tation of arm movemen	ıt, n (%)		
Grad	de 0			
Grad	de 1			
Grad	de 2			
Grad	de 3			
	p-value =			
Note:	- On any day (by cas	es)		
	- Grading	,		
	Grada 0 por	no		
	Grade 1 mi	le Id		
	Grade 2 mg	nderate		
	Grade 3 - set	nere		
	Grade 5 - sev			

Number of Days by Local Reaction	Tri fluvac (N = xx)	Comparator (N = xx)	
Pain			
only 30 min.	xx (xx.xx)	xx (xx.xx)	
1 day	xx (xx.xx)	xx (xx.xx)	
2 days	xx (xx.xx)	xx (xx.xx)	
3 days	xx (xx.xx)	xx (xx.xx)	
p-value = x.xxxx			
Limitation of arm movement			
only 30 min.	xx (xx.xx)	xx (xx.xx)	
1 day	xx (xx.xx)	xx (xx.xx)	
2 days	xx (xx.xx)	xx (xx.xx)	
3 days	xx (xx.xx)	xx (xx.xx)	
p-value = x.xxxx			

TREF 3.8: Comparison Number of Subject by Number of Local Reaction Days at Post Immunization GPO Tri fluvac and Active Comparator Group

Note: - Subjects who had symptom with local reaction will be considered in this table.

- Number of subjects who had symptom will be compared between Tri fluvac and comparator.

- Percentage will be calculated from total enrollment subject.

TREF 3.9: Comparison Number of Subjects by Number of Local Reaction at Post Immunization
GPO Tri fluvac and Active Comparator Group

Number of Local Reaction	Tri fluvac (N = xx)	$\begin{array}{l} \textbf{Comparator} \\ \textbf{(N = xx)} \end{array}$
No symptom	xx (xx.xx)	xx (xx.xx)
1 symptom	xx (xx.xx)	xx (xx.xx)
2 symptoms	xx (xx.xx)	xx (xx.xx)
p-value = x.xxxx		

Note: - All enrollment Subjects will be considered in this table. - Percentage will be calculated from total enrollment subject.

TREF 3.10: Comparison of Maximum Grade of Any Systemic Reaction at Post Immunization by GPO Tri fluvac and Active Comparator Group

Create	Tri fluvac	Comparator	
Grade	(N=xx)	(N=xx)	
	n (%)	n (%)	
Grade 0	xx(xx.xx)	xx(xx.xx)	
Grade 1	xx(xx.xx)	xx(xx.xx)	
Grade 2	xx(xx.xx)	xx(xx.xx)	
Grade 3	xx(xx.xx)	xx(xx.xx)	
P-value = x.xxxx			

Note: Grading

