Appendix 04: Listing of Local Reaction at Post Immunization

Appendix 05: Listin	g of Systemic Reaction a	at Post Immunization
---------------------	--------------------------	----------------------

Observe	Subject Number	Study Group	Symptom	Follow up Day (Grade)
1				
2				
3				

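### The SAP's any-local-reaction table leaves out erythema and induration, which belong to the primary safety endpoint; separately, two AE tables count probably-not-related events as related

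*SAP*

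**What the plan says.** Protocol section 3 (Primary Safety Endpoints) lists "Solicited local adverse events, including redness / erythema, swelling / induration, pain, and limitation of arm movement within 30 minutes of vaccination" and over Days 0-3. The SAP synopsis repeats the same four items. It asks for an any-local summary by severity and promises that "Percentages of participants experiencing each reaction or event, or at least one reaction or event will be calculated along with two-sided exact 95% CIs". It adds that "The percentage of participants with solicited AE and SAEs will be compared between vaccine and comparator groups", at a two-sided 0.05 level.

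The SAP shells differ. TREF 3.5 is described as any local reaction on any day, by case, yet carries the note "Erythema and Induration will be not included". FREF 07 has the same note. TREF 3.6 does show erythema, swelling and induration, but as measurements in cm under the note "Summary by case who had symptoms".

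On causality, the notes to TREF 2.1 and 2.4 define events suspected to be related as those rated probably not, probably or definitely related. Protocol 8.7 has two categories, Related and Not related.

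**The concern.** Solicited local reactions are a primary safety endpoint. A participant whose only local reaction is erythema or induration would appear in TREF 3.5 as Grade 0, meaning none. If the vaccines differ in how often they cause these reactions, the difference would show only as counts per time point in TREF 3.6. No table would give the percentage of participants affected over Days 0-3, or compare it between arms.

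The causality point works the other way. If a probably-not-related category is collected, the related AE counts in TREF 2.1 and 2.4, and the related SAE count in TREF 2.1, can only be inflated against the protocol's definition. If it is not collected, the shells do not match the data.

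**Working it through.** There is no plan figure to reproduce. The main check sets the shells against the definition.

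**1. What each local-reaction shell covers**

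| Shell | Pain, arm movement | Erythema | Swelling | Induration |
|---|---|---|---|---|
| TREF 3.5 (FREF 07 has the same note) | max grade 0-3 | excluded | not stated | excluded |
| TREF 3.6 | n (%) per time point | n and cm, affected cases | n and cm, affected cases | n and cm, affected cases |
| TREF 3.7 | max grade 0-3 | no row | no row | no row |
| TREF 3.8 | number of days | no row | no row | no row |
| TREF 3.9 | counts up to 2 symptoms | no room | no room | no room |

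- In TREF 3.6 the p-value for the size-measured reactions sits under the cm summary. It compares size among those affected, not how often the reaction occurs.
- TREF 3.5 to 3.9 show no confidence interval, although the synopsis promises exact ones.
- TREF 3.5 and 3.7 stop at Grade 3. Protocol 8.2 says solicited reactions are graded by Appendix A, which defines Grade 4 for pain, erythema and induration/swelling. The SAP's own temperature tables (TREF 3.1, 3.2) do have a Grade 4 row.
- Protocol 11.3.2 and 11.4 omit limitation of arm movement but keep erythema and swelling/induration, so they do not support the exclusion.

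**2. Direction of the effect**

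Let A be participants with at least one reaction counted in TREF 3.5, and B those with erythema or induration.

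Defined rate = P(A or B) = P(A) + P(B and not A). Reported rate = P(A). Shortfall = P(B and not A), which is never negative. The maximum grade can likewise only be lowered: a participant with Grade 1 pain and Grade 3 erythema is shown as Grade 1.

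**3. Scale (assumed rates, not from the documents)**

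Shortfall in participants = assumed rate × arm size.

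- 1%: 0.01 × 630 = 6.3; 0.01 × 315 = 3.2
- 5%: 0.05 × 630 = 31.5; 0.05 × 315 = 15.8

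An assumed range of 0-5% gives 0-32 Tri Fluvac and 0-16 comparator recipients.

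**4. Swelling, which TREF 3.7 to 3.9 drop**

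Protocol 2.4 reports swelling in 2.5% of 200 phase I/II vaccinees: 0.025 × 200 = 5. The exact (Clopper-Pearson) 95% CI for 5/200 is 0.82% to 5.74%. Applied to 630: 0.025 × 630 = 15.8, or about 16, with a range of about 5 to 36. This shows how many participants those tables might miss. It does not bound the error in TREF 3.5, whose note does not name swelling.

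**5. Causality**

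Protocol 8.7 places an event with another more likely cause under Not related. Its Related category reaches down only to an equally likely cause. Read in its ordinary sense, *probably not related* means another cause is more likely, so it falls under Not related; TREF 2.1 and 2.4 put it under related. TREF 2.5 and protocol 6.2 use *definitely related*, a level 8.7 does not define. The documents give no event counts by causality level, so this effect cannot be computed.

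**The case against.** The best reply is that little is lost and part of the case is conditional.

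- **Reported elsewhere.** TREF 3.6 gives n per arm and time point, Appendix 04 lists local reactions by day and grade, and the synopsis text on exact intervals still binds even where a shell has no CI column. This stands in part: it is a gap in the summary tables, provided the listing includes erythema and induration, which its shell does not state. An any-day rate cannot be obtained from counts per time point.
- **Small reactions and overlap.** Appendix A starts erythema at 2.5 cm, so smaller reactions would have no grade even without the exclusion. It also treats induration and swelling as one entry, so some induration might survive through swelling in TREF 3.5. Both points limit how far the graded result would move. Neither restores erythema to the composite.
- **Causality.** *Probably not related* is not a protocol term, the CRF scale is not in the documents, and over-counting related events looks conservative. Investigators need not judge causality for solicited events with onset in the solicitation period, and TREF 2.1 and 2.4 carry no p-value. So a miscount is not demonstrated. The conflict in definitions is, and counting unrelated events in both arms can dilute a difference.
- **Consequence.** No safety success threshold depends on TREF 3.5. That is correct, and it limits the severity.

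**Conclusion.** The concern holds. As written, the SAP does not deliver the solicited local endpoint that it and the protocol define, and no other part of the plan repairs this. The any-local rate is understated by the proportion of participants whose only local reaction is erythema or induration. That proportion is unknown; the 0-5 percentage point range rests on assumption alone. The causality conflict also holds, as a mismatch of definitions whose numerical effect depends on the scale the CRF collects. The immunogenicity non-inferiority conclusion is untouched. This should be fixed, but it does not threaten the trial's main result.

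**What to change.** For local reactions:

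- Delete the exclusion notes in TREF 3.5 and FREF 07.
- Add erythema/redness and swelling/induration to TREF 3.5, 3.7, 3.8, 3.9 and FREF 07 as n (%) of participants over Days 0-3, using the recorded Appendix A grade, with a Grade 4 row in the graded tables and the promised exact 95% intervals.
- State in a footnote how a reaction below the Grade 1 size is shown; reporting it as present, separate from none, would avoid hiding it. State also which scale grades limitation of arm movement, since Appendix A as shown has none.
- Make protocol 11.3.2 and 11.4 agree with section 3 and the SAP synopsis on limitation of arm movement, so that any local AE has one definition.

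For causality, tabulate related AEs and SAEs by the two categories in protocol 8.7, with a stated mapping if the CRF collects a finer scale. Reconcile the *definitely related* wording in TREF 2.5 and protocol 6.2 with 8.7.

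The cost is SAP shell and footnote edits plus wording alignment in the protocol. No new visits or assessments are needed. The any-local rate may look slightly less favourable.

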# **5.3 Treatment Assignment Procedures**

# 5.3.1 Randomization Procedures

This is a double-blind, randomized, and controlled trial with two groups: vaccine and comparator. Each participant will be assigned a unique screening number assigned by the investigator after signing the informed consent. After an individual is determined to be eligible for study participation, the participant will be randomized by assigning a unique participant identification number from the randomization schedule.

The complete randomization schedule that contains the participant identification number and the corresponding randomization assignment will be produced using computer software prior to the initiation of the study. The permuted randomized block design procedure will be used to generate the randomization schedules using varying block sizes. Treatment assignments will be completely randomized within each block, and the blocks will be ordered (permuted) randomly to ensure treatment balance during enrollment and maintenance of the blind.

The Investigator will maintain a screening/enrollment log. The log will contain essential information including participant ID number, date of screening, gender, date of birth, whether or not the participant meets eligibility criteria, whether the participant is enrolled and date, and if not enrolled, reason why the participant was not enrolled or not randomized.

Once a participant identification number has been assigned, it will not be used again. Additional participants may be randomized into the study in the case of any participant who is randomized but does not receive any study vaccine. Study participants will be randomly assigned to one of the two treatment groups. Blinding through randomization number will be maintained for the investigator who assesses immunogenicity and safety.

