#### 7.2 Study Visits: Screening Visit

Screening: At the screening visit, prior to perform any study specific procedures, the Investigator and/or designated staff must provide all information related to the study to the subjects. Subjects must have enough time to read the Informed Consent Forms which have been approved by an Ethics Committee and ask questions. If the subjects are interested to participate in the study, they shall sign and date in the Informed Consent Form thereafter. The investigator or delegate who involves in the consent process shall check the completion of the consent forms and then sign and date on the same day of signing by the subject. A copy of the signed informed consent form will be given to each participant for his/her records.

After signing of informed consent form, all subjects will be screened for eligibility through medical history review and physical examination. All volunteers will be checked against the inclusion/exclusion criteria.

The screening assessments will be performed up to 30 days prior to the first vaccination.

The screening procedures for the study included a medical history, vital signs, and physical examination will be performed. A urine pregnancy test will be done in females. Female volunteers should avoid pregnancy at least 60 days after the vaccination by using an effective birth control method. They will be provided pregnancy counseling and the contraceptive pills or injection will be VED offered for free. Participants who meet eligibility criteria will be enrolled. 3 ml blood samples will be collected prior to vaccination.

MAHIDOL UNIVERSITY

ตยาลัยม

7.3 Vaccination (can be the same day as screening day): A single dose of a seasonal trivalent inactivated split virion influenza vaccine [A/Michigan/45/2015 (H1N1) pdm09-like virus, A/Hong Kong/4801/2014 (H3N2)-like virus, and B/Brisbane/60/2008-like virus] in GPO Tri Fluvac and comparator will be given to all subjects after blood collection for immunology assays. The vaccine will be administered via the intramuscular route; the preferred injection site will be the deltoid of the non-dominant arm. After vaccination volunteers will remain at the clinic for at least 30 minutes to observe for any reactogenicity after immunization. A diary card will be provided to the subjects for recording such events for 3 days after vaccination (Day 1-3).

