#### 11.3 Data Analysis

#### **11.3.1 General Data Analysis Considerations Analysis Populations**

All subjects who receive one vaccination will be included in the safety population. This population will be used in the evaluation of safety and tolerability.

The immunogenicity analysis will be conducted based on an intent-to-treat (ITT) analysis. The population for the intent-to-treat analysis is defined as all individuals in the trial. The intent-to-treat analysis will include individuals who do not comply with the protocol-defined treatment schedule; that is, the intent-to-treat analysis will include individuals who may not complete the vaccination and follow-up.

As there might be some individuals who did not comply with the protocol-defined treatment schedule, a per-protocol analysis (PPA) will also be conducted. The population for the per protocol analysis is defined as individuals who meet all inclusion and exclusion criteria, and complete the treatment schedule.

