Fatigue	only 30 min.		
	1 day		
	2 days		
	3 days		
	4 days		
	5 days		
	p-value =	X.XXXX	
Malaise	only 30 min.		
	1 day		
	2 days		
	3 days		
	4 days		
	5 days		
	p-value =	X.XXXX	
Chills	only 30 min.		
	1 day		
	2 days		
	3 days		
	4 days		
	5 days		
	p-value =	X.XXXX	
Myalgia	only 30 min.		
	1 day		
	2 days		
	3 days		
	4 days		
	5 days		
	p-value =	X.XXXX	

TREF 3.13: Comparison Number of Subject by Number of Systemic Reaction Days at Post Immunization GPO Tri fluvac and Active Comparator Group

Number of Days by Systemic Reaction		Tri fluvac (N=xx)	Comparator (N=xx)	
Arthralgia	only 30 min.	XX(XX.XX)	XX(XX.XX)	
	1 day	xx(xx.xx)	xx(xx.xx)	
	2 days	xx(xx.xx)	xx(xx.xx)	
	3 days	xx(xx.xx)	xx(xx.xx)	
4 days		xx(xx.xx)	xx(xx.xx)	
	5 days	xx(xx.xx)	xx(xx.xx)	
p-value = x.xxxx				
Nausea	only 30 min.			
	1 day			
	2 days			
	3 days			
	4 days			
	5 days			
	p-value = x.xxxx			
Vomiting	only 30 min.			
	1 day			
	2 days			
	3 days			
	4 days			
	5 days			
	p-value = x.xxxx			
Rash	only 30 min.			
	1 day			
	2 days			
	3 days			
	4 days			
	5 days			
	p-value = x.xxxx			

TREF 3.13: Comparison Number of Subject by Number of Systemic Reaction Days at Post Immunization between GPO Tri fluvac and Active Comparator Group (Continue)

Note: - Subjects who had symptom with Systemic reaction will be considered in this table.

- Number of subjects who had symptom will be compared between Tri fluvac and comparator.

- Percentage will be calculated from total enrollment subjects.

Number of Local Reaction	Tri fluvac (N=xx)	Comparator (N=xx)	
No symptom	xx(xx.xx)	xx(xx.xx)	
1 symptom	xx(xx.xx)	xx(xx.xx)	
2 symptoms	xx(xx.xx)	XX(XX.XX)	
3 symptoms	xx(xx.xx)	xx(xx.xx)	
4 symptoms	xx(xx.xx)	xx(xx.xx)	
5 symptoms	xx(xx.xx)	xx(xx.xx)	
6 symptoms	xx(xx.xx)	xx(xx.xx)	
7 symptoms	xx(xx.xx)	xx(xx.xx)	
8 symptoms	xx(xx.xx)	xx(xx.xx)	
9 symptoms	xx(xx.xx)	xx(xx.xx)	

TREF 3.14: Comparison Number of Subjects by Number of Systemic Reaction at Post Immunization between GPO Tri fluvac and Active Comparator Group

Note: - All enrollment Subjects will be considered in this table.

- Percentage will be calculated from total enrollment subject.

4. Immunogenicity

TREF 4.1: Comparing Seroconversion Rates between GPO Tri fluvac and Active Comparator Group Separated by HI Assay at Day 21 and 90

TREF 4.2: Comparing Seroconversion Rates between GPO Tri fluvac and Active Comparator at Any Day

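### Four SAP reaction tables take percentages from total enrolment and leave no place for subjects not assessed, which conflicts with the protocol's vaccinated safety population

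*SAP*

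**What the plan says.** **SAP, section 3 (Post Immunization Reaction).** TREF 3.9 counts local reactions per subject in the rows *No symptom*, *1 symptom* and *2 symptoms*. Its note says "All enrollment Subjects will be considered in this table. - Percentage will be calculated from total enrollment subject". TREF 3.14, the systemic counterpart, has the same note and rows from *No symptom* to *9 symptoms*. Neither table has a row for missing or unassessed subjects.

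TREF 3.8 tabulates days with a local reaction. Its rows cover only affected subjects ("Subjects who had symptom with local reaction will be considered in this table"), but the denominator is again enrolment: "Percentage will be calculated from total enrollment subject". TREF 3.13 does the same for systemic reactions: "Percentage will be calculated from total enrollment subjects".

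**Protocol, section 11.3.1.** The set for safety and tolerability is defined by vaccination: "All subjects who receive one vaccination will be included in the safety population".

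**Protocol, enrolment and vaccination.** Section 7.2 ties enrolment to eligibility: "Participants who meet eligibility criteria will be enrolled". Section 5.3.1 foresees a gap between randomisation and injection: "Additional participants may be randomized into the study in the case of any participant who is randomized but does not receive any study vaccine".

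**Protocol, source of the data.** Under section 8.2, staff assess reactions at 30 minutes and the participant then records three days in a diary. Section 7.4.1 has the diary returned at the Day 7 visit.

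**The concern.** Two kinds of enrolled subject have no complete reaction record: those never injected, and those vaccinated but lost before the diary is returned. If every enrolled subject must be in TREF 3.9 and 3.14, the only row open to someone with no recorded reaction is *No symptom*. In TREF 3.8 and 3.13 the same person is absent from the rows but present in the denominator. In all four tables the percentage with a reaction falls below the percentage among people whose reactions were observed.

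Solicited reactions are a primary safety endpoint, and section 11.4 of the protocol compares them between arms at a two-sided 0.05 level. A layout that treats no information as no reaction makes both vaccines look slightly better tolerated than the data show. If loss differs by arm, it favours the arm with more loss.

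**Working it through.** **1. Does the enrolled set differ from the vaccinated set?** The documents allow for it. Section 5.3.1 refers to "any participant who is randomized but does not receive any study vaccine". SAP TREF 1.5 has a *Positive* row for the Day 0 pregnancy test under its *Enrolled* heading, while protocol section 8.12.1 bars injection after a positive test. The documents expect such people to be possible but give no count.

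**2. Does another rule settle missing diaries?** No. The data considerations in protocol section 11.3.1 leave missing-data procedures to the final analysis report. The SAP can show missingness where it chooses to: TREF 2.9 has *Not done* and *Inconclusive* rows for swabs. TREF 3.9 and 3.14 have nothing similar.

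**3. The planned denominator.** Inputs from protocol section 11.2: H3 seroconversion 0.535 in both arms, margin 0.10, one-sided alpha 0.025, power 80%, ratio 2:1.

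- Comparator n = (1.960 + 0.842)² × 0.535 × 0.465 × (1 + 1/2) / 0.10² ≈ 293; vaccine 2 × 293 = 586; total 879.
- Allowing for 7%: 293/0.93 = 315.1, 586/0.93 = 630.1, 879/0.93 = 945.2.

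This reproduces the plan's 315, 630 and 945.

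**4. Dilution.** Let r be the reaction rate among assessed subjects and m the share of enrolled subjects with no reaction data. Then

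shown rate = r × (1 − m), shortfall = r × m, relative understatement = m.

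For r, take 32.5%, the pain rate in vaccine recipients of the earlier Tri Fluvac trial (protocol section 2.4). For m, the documents give nothing, so a range is shown:

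| m (assumed) | Subjects, of 630 / 315 | Shown rate | Shortfall (points) |
|---|---|---|---|
| 1% | 6 / 3 | 32.2% | 0.3 |
| 2% | 13 / 6 | 31.9% | 0.7 |
| 5% | 32 / 16 | 30.9% | 1.6 |
| 7% | 44 / 22 | 30.2% | 2.3 |

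The 7% is the plan's allowance for subjects outside the ATP cohort (described elsewhere as loss to follow-up), so it is an upper scenario for a three-day diary. The formula is also a ceiling on the dilution: a subject with no diary who reacted at 30 minutes is still counted.

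**5. Between arms.** Equal loss multiplies both rates by the same (1 − m) and leaves their ratio unchanged. For an extreme unequal case, assume equal true rates of 32.5%, 7% loss on Tri Fluvac and none on the comparator. The tables would show 30.2% against 32.5%, a spurious difference of 2.3 points. At a rate of 30%, the standard error of the difference is √[0.30 × 0.70 × (1/630 + 1/315)] = 0.032, or 3.2 points. The artefact is about 0.7 of a standard error.

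**The case against.** The strongest reply is that the SAP nowhere says a missing diary means no reaction. That is correct: the consequence follows from the rows offered and the stated denominator. Appendix 01 also provides a listing of subjects excluded from analysis. But a listing does not change the four notes, which state a denominator outright.

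Second, *enrolled* may be loose labelling for anyone who is not a screen failure. TREF 1.1 to 1.4 use it as the heading opposite *Screen Failed*, and a similar note recurs under titre tables where a subject without serum cannot contribute. Screening and vaccination may also fall on the same day. This weakens the part about unvaccinated subjects but leaves the missing-diary part untouched.

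Third, a reader might infer that all solicited-reaction rates are understated. The documents do not support that. The enrolment wording is confined to TREF 3.8, 3.9, 3.13 and 3.14. The tables by reaction, grade and time point (TREF 3.5 to 3.7 and 3.10 to 3.12) do not carry it, and the TREF 3.14 shell shows no p-value.

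Fourth, the protocol limits the loss: staff check every vaccinated subject at 30 minutes, section 5.5 requires efforts to recall non-attenders, section 7.5 asks for diary review on exit before Day 7, and section 5.4.4 expects few withdrawals. All of this stands and points to a small m.

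**Conclusion.** The conflict is real and limited to four tables. Their notes take percentages from total enrolment, whereas the protocol's safety population is the vaccinated, and two of the tables force every enrolled subject into a symptom-count row. Followed literally, the rates are reduced by a relative amount of up to m. On an assumed 32.5% rate that is 0.3 points at m = 1% and 2.3 points at m = 7%. It is zero if every enrolled subject was vaccinated and returned a complete diary.

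Two stronger conclusions are tempting. One is that the SAP imputes missing reactions as none by an explicit rule; it does not. The other is that the layout would readily create or hide a significant difference between arms. Even the extreme 7% against 0% case gives less than one standard error, and no document suggests that loss would differ by arm. The change is still worth making, because it costs almost nothing and concerns a primary safety endpoint.

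**What to change.** In the notes to TREF 3.8, 3.9, 3.13 and 3.14, replace total enrolment with the vaccinated safety population that has reaction data for the period shown. Then:

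- Add a row, by arm, for subjects not assessed or with an incomplete diary.
- Assign *No symptom* only when the 30-minute check and all three diary days are available and negative.
- Count any observed reaction as a reaction, even if the diary is incomplete.
- Leave subjects in the new row out of the percentage denominator, and give a sensitivity count that includes them.
- Use the same denominator in TREF 3.5 to 3.7 and 3.10 to 3.12, whose notes leave it open.

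The sensitivity count matters because an analysis of available diaries is itself biased if reactions cause drop-out. With 32.5% among the assessed and 7% unassessed, the rate lies between 0.93 × 32.5% = 30.2% (none of the unassessed reacted) and 30.2% + 7% = 37.2% (all of them did).

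The cost is a change to the table notes and one extra row, with no new data and no change to visits. Denominators become slightly smaller and reported rates slightly higher. If no record is incomplete, the new row shows zero and documents that.
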